**Figure 3. Safety Reporting Overview** 

# Safety Reporting Overview

\* Unless identified in the protocol as not requiring immediate reporting

# 9 ASSESSMENT AND FOLLOW-UP

# 9.1 COLLECTING FOLLOW-UP INFORMATION

The following information will be ascertained at the time of death or discharge or at 28 days after randomisation (whichever is sooner):

- Vital status (alive / dead, with date and presumed cause of death, if appropriate)
- Hospitalisation status (inpatient / discharged, with date of discharge, if appropriate)
- Use of ventilation (with days of use and type, if appropriate)
- Use of renal dialysis or haemofiltration

This information will be obtained and entered into the web-based IT system by a member of the hospital clinical or research staff. Follow-up information is to be collected on all study participants, irrespective of whether or not they complete the scheduled course of allocated study treatment. Study staff will seek follow-up information through various means including medical staff, reviewing information from medical notes, routine healthcare systems, and registries.

#### 9.2 DURATION AND MODE OF FOLLOW-UP

All randomised participants are to be followed up until death, discharge from hospital or 28 days after randomisation (whichever is sooner). It is recognised that in the setting of this trial, there may be some variability in exactly how many days after randomisation, information on disease status is collected. This is acceptable and will be taken account of in the analyses and interpretation of results, the principle being that some information about post-randomisation disease status is better than none.

Where discharge occurs before 14 days, study medication will be sent home with patient. The study team will send a pre-paid envelope to the patients to return any unused medication and empty bottles if patients are not able to attend Day 14 and Day 28 visits in person.

Where discharge occurs before 28 days, patients will be invited to return weekly for monitoring of blood tests to confirm continued recovery from illness. Where this is not possible, monitoring of clinical status will be achieved by telephone.

Longer term (up to 10 years) follow-up will be sought through linkage to electronic healthcare records and medical databases including those held by NHS Digital, Public Health England and equivalent bodies, and to relevant research databases (e.g. UK Biobank, Genomics England).

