#### 3 STUDY DESIGN

This is a multi-site, two stage, open label, randomized (1:1:1) controlled trial.

Figure 2. Schematic of study design

Treatment is for 14 days from baseline. Patients will receive follow-up assessment at 7, 14 and 28 days after the first dose.

The time allowed for screening assessments allows time for eligibility assessments to be included.

- Screening Period: up to 7 days to the day randomisation
- Treatment Period: 14 days

MATIS version 4.0 dated 2nd November 2022

IRAS: 282552 Page **22** of **57** 

Imperial College Healthcare

- Follow-up period: Day 14 to 28

Patients who have recovered and are fit for discharged from hospital during the treatment period, will be discharged home with trial medication to complete a fixed 14 day course. Such patients will be followed up weekly with telephone monitoring until day 28 and additional blood test monitoring where practically possible.

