#### **SAEs**

An SAE form should be completed and faxed to the study coordination centre for all SAEs within 24 hours. However, relapse and death due to <condition>, and hospitalisations for elective treatment of a pre-existing condition do not need reporting as SAEs.

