**Table 7. Schedule of events** 

	Screening	Baseline				Last visit
Study Day	-6 to 0	0	1 *	7 #	14#	28#
Time window		- 2 days	+ 1 day	± 3 days	± 3 days	± 3 days
Informed consent	х					
Inclusion/Exclusion criteria	х	Х				
Demographic data	х					
Medical history including major comorbidities	х					
Physical exam	х					
COVID-19 diagnosis, duration and severity	х					
Pregnancy test	х					
Vital signs	х	Х	Х	Х	Х	Х
NEWS score	х	Х	Х	Х	х	Х
Inflammatory markers (CRP, D-dimer, LDH, ferritin, full blood count)		х	Х	х	х	Х
PK levels*					х	Х
Full blood count ¶ (FBC)		Daily while on CYP3A4 inhibitor				
Coagulation, Chemistry, Ferritin, Troponin, Procalcitonin	х	х	x	x	х	х
FiO 2	х	Х	Х	х	х	Х
SpO₂ and/or PaO₂	х	Х	х	х	х	Х
Randomisation		Х				
Weight and Estimated height		Х				
Safety monitoring of liver and renal function	х	Х	Х	Х	х	Х
Length of stay						
Serious Adverse Events	х	Х	Х	х	х	х
Concomitant medications	Х	Х	Х	х	Х	Х
Serum		х		х	Х	х
Plasma		Х		х	Х	Х
RNA in PAXgene tube		Х		Х	Х	Х
PBMC		x		х	х	Х

<sup>+ data that is routinely collected for clinical purposes will be recorded and a visit is not required

<sup># in the event that the patient recovers from COVID19 and is discharged, these visits will not be mandated. Instead a visit should occur on the date of discharge. Where possible, patients will be contacted by telephone at day 7, 14 and 28 and invited to attend for blood tests to monitor resolution of illness.

\*Ruxolitinib dose for these patients will be assessed after 10 dialysis patients complete Day 14 through pharmacokinetics (PK) levels which will be assessed.

<sup>¶For patients randomized to ruxolitinib and prescribed a strong CYP3A4 inhibitor or dual CYP3A4/CYP2C9 inhibitor. Please refer to Section 7.8 for details.

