1.1.3 Secondary outcomes of the main study

Each of the outcomes below at 14 and 28 days between RUX or FOS versus SOC:

- Change in severity on the modified WHO COVID-19 Ordinal Scale (3 or 4 to 5,6,7,8,9)
- Mortality (Y/N)
- Invasive ventilation (Y/N)
- ECMO (Y/N)
- Non-invasive ventilation including CPAP and high flow nasal oxygen (Y/N)
- Renal replacement therapy (Y/N)
- Venous thromboembolism (Y/N)
- Inflammatory markers CRP, LDH, ferritin, D-dimer (units)
- Length of stay (days)
- Serum creatinine (units).

• Re-admission data – were they readmitted within 28 days? (from free text in SAEs)

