3.2.3 Components of the modified WHO COVID-19 score

The following outcomes will be examined at day 14 and day 28 by replacing the primary outcome in the main analysis model as described in section 3.1.3:

- Death (yes/no)
- Requirement for invasive ventilation plus organ support (yes/no)
- Invasive ventilation (yes/no)

- Non-invasive ventilation including CPAP and high flow nasal oxygen (yes/no)
- Renal replacement therapy (yes/no)
- Venous thromboembolism (yes/no)

Each model will be fitted on complete cases and no imputation of missing values or sensitivity analysis will be undertaken.

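### Protocol 9.1 and 9.2 end follow-up at discharge, against home dosing to day 14 and 28-day endpoints elsewhere, so capture after discharge is contradictory and not guaranteed

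*Protocol*

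**What the plan says.** Two passages stop at discharge. Protocol 9.2 begins: "All randomised participants are to be followed up until death, discharge from hospital or 28 days after randomisation (whichever is sooner". Protocol 9.1 says that vital status, hospitalisation status, ventilation and dialysis "will be ascertained at the time of death or discharge or at 28 days after randomisation (whichever is sooner".

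Other passages carry on:

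- Protocol 3, repeated in SAP 1.2, says of patients sent home during the treatment period: "Such patients will be followed up weekly with telephone monitoring until day 28".
- A later paragraph of Protocol 9.2 invites anyone discharged before day 28 back each week for blood tests, with a telephone check if they cannot come.
- Protocol 9.5 commits the team to reasonable efforts to reach discharged participants, and 11.4 sets safety assessments at days 7, 14 and 28.
- Protocol 7.16 continues study drug at home after early discharge. SAP 1.8 places the final analysis after 28 days of follow-up for all.
- The Table 7 footnote says of discharged patients: "these visits will not be mandated. Instead a visit should occur on the date of discharge". It makes telephone contact at days 7, 14 and 28 conditional on being possible.

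Protocol 3.3 and SAP 1.1.3 set the secondary endpoints at 14 and 28 days. SAP 1.1.3 adds readmission: "were they readmitted within 28 days? (from free text in SAEs". Protocol 8.4 exempts "relapse and death due to <condition>" from SAE reporting, with the condition never filled in. SAP 3.2.3 says of the models for death, ventilation, renal replacement therapy (RRT) and VTE: "Each model will be fitted on complete cases and no imputation of missing values or sensitivity analysis will be undertaken".

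**The concern.** A site that takes the first sentence of 9.2 and the timing in 9.1 at face value has finished with a participant on the day of discharge. That participant may still be taking study drug and can still die, clot, need dialysis or be readmitted before day 28. A second site, working from section 3, would telephone every week. Both follow the protocol, yet they would deliver different 28-day data.

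Time to discharge is itself an efficacy endpoint (SAP 3.2.4), so a drug that works may change how long people are observed in hospital. If observation weakens at discharge, completeness of the 28-day outcomes can then depend on treatment. Safety information from dosing at home is at stake in the same way.

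**Working it through.** **1. The plan's own figures.** Inputs (Protocol 4.1, SAP 1.5): 50% vs 30%; one-sided alpha 0.25 at stage 1 and 0.027 at stage 2; 57 then 152 per arm; 5% missing, so 54.15 then 144.4 evaluable. Power = Φ[(δ − z·se0)/se1], with se0 = √(2 × 0.4 × 0.6/n) and se1 = √((0.25 + 0.21)/n).

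- Stage 1: (0.2 − 0.6745 × 0.0942)/0.0922 = 1.48, power 0.931 (stated 92%).
- Stage 2 alone: (0.2 − 1.927 × 0.0577)/0.0564 = 1.58, power 0.942.
- Both stages, correlation √(54.15/144.4) = 0.612: 0.895 (stated 90%).
- Family-wise error with two comparisons correlated 0.5: 0.0489 (stated maximum 5%).

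These reproduce, and none uses post-discharge data. The stated design is not affected.

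**2. When follow-up ends.** Protocol 9.1 and the opening of 9.2 say discharge, if it comes before death or day 28. Protocol 3, the rest of 9.2, 11.4 and SAP 1.2 and 1.8 say day 28. Table 7 says day 28 if the patient can be reached. These cannot all be the rule.

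**3. Which outcomes have a route after discharge.**

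- Death, ventilation and RRT are in the 9.1 list, and 9.1 names notes, routine systems and registries as sources. Protocol 8.5 collects all deaths. Only the timing is in conflict.
- VTE, readmission and SAEs are not in the 9.1 list. The post-discharge contacts in 9.2 and Table 7 are described as blood tests and checks on recovery, not as collection of these endpoints.
- Readmission can only follow discharge, and SAP 1.1.3 and 2.8 take it only from SAE free text. The unfilled exemption in Protocol 8.4 leaves open whether a COVID-19 readmission needs an SAE form.

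**4. What the analysis does.** SAP 3.2.3 uses complete cases but does not say whether a discharged participant with no day-28 contact is missing or event-free. Let d be the share discharged alive and event-free, q their event risk to day 28, c the share of these participants captured, and R the true 28-day risk.

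- Counted event-free: risk is understated by d·q·(1 − c).
- Dropped: risk is overstated by d(1 − c)(R − q)/[1 − d(1 − c)], when q is below R.

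The two errors have opposite signs, and both differ by arm if d or c does. The documents give none of d, q, c or R.

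**5. Illustration, all rates assumed.** Take deaths, discharge in 80% (standard of care) and 85% (drug), q = 1% to 3% in both arms, no capture, and the uncaptured counted as alive. Missed deaths per 152: 121.6 × q = 1.2 to 3.6 and 129.2 × q = 1.3 to 3.9. The error in the risk difference is 0.05 × q = 0.05 to 0.15 percentage points.

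**6. A related mismatch.** Protocol 4.2 treats discharge before day 14 as event-free unless other data show otherwise. SAP 3.1.2 makes the assumption without that exception. SAP 3.1.3 takes its missing-data method from 3.1.2, and 3.2.1 reuses 3.1.3 for the 28-day outcome.

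**The case against.** The strongest reply is that follow-up after discharge is already planned. Section 9.2 itself supplies weekly return visits with a telephone fallback that carries no condition. In section 3 the practicality qualifier attaches to blood tests, not to calls. Only the Table 7 footnote makes calls conditional. Hospitalisation is a seriousness criterion in Protocol 8.1 and SAE forms are due within 24 hours, so an unplanned readmission has a reporting route. Readmission is only summarised by arm in SAP 2.8 and is not among the outcomes modelled in SAP 3.2. The case report form is not available, so what sites actually close at discharge cannot be known.

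All of this stands, and it rules out two stronger readings. A reader might infer that deaths, clots and readmissions after discharge will not be seen at all; the contacts just listed contradict that. A reader might also infer that complete-case analysis removes every discharged participant and so grossly distorts 28-day mortality. No passage instructs this: 9.1 records vital status and discharge date, and SAP 3.2.3 does not define discharged participants as missing.

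The reply does not remove the contradiction between the two stopping rules. Nor does it supply a required contact that asks about VTE, readmission and SAEs, or a rule for discharged participants who are not reached.

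**Conclusion.** The point holds as an inconsistency with consequences for the 28-day outcomes. The wording in 9.1 and at the start of 9.2 is a wrong rule given the endpoints and home dosing, and the other passages correct it only in part. VTE, readmission and SAEs at home are most exposed; death and RRT less so.

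The size of any bias is unknown. Its direction would depend on a choice that the SAP does not state. On the assumed rates above, the effect on mortality is small if uncaptured participants are counted as alive; it would be larger if many were dropped. The argument for bias rests on time to discharge, or completeness of contact, differing between arms, which is possible but not shown. Sample size, stated power and error rate stand. This should be fixed, but it does not undermine the primary analysis.

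**What to change.** - In Protocol 9.1 and 9.2, remove discharge as an end of follow-up, so that it ends at death or day 28 whatever the discharge status.
- Make a telephone or record check at days 14 and 28 the required minimum in all arms, and align the Table 7 footnote. It should cover vital status, ventilation, RRT, VTE, readmission and SAEs.
- Reconcile the unfilled placeholder in Protocol 8.4 with the use of SAE reports as the source for readmission.
- In SAP 3.2.3, take the day-28 component outcomes of discharged participants from that contact.
- Give the early-discharge rule in SAP 3.1.2 the exception for contrary data that Protocol 4.2 already has.

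The cost is wording in both documents and more calls and record chasing by site staff. The calls and the record sources are already described, so the added burden is small.

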**Table 7. Schedule of events** 

	Screening	Baseline				Last visit
Study Day	-6 to 0	0	1 *	7 #	14#	28#
Time window		- 2 days	+ 1 day	± 3 days	± 3 days	± 3 days
Informed consent	х					
Inclusion/Exclusion criteria	х	Х				
Demographic data	х					
Medical history including major comorbidities	х					
Physical exam	х					
COVID-19 diagnosis, duration and severity	х					
Pregnancy test	х					
Vital signs	х	Х	Х	Х	Х	Х
NEWS score	х	Х	Х	Х	х	Х
Inflammatory markers (CRP, D-dimer, LDH, ferritin, full blood count)		х	Х	х	х	Х
PK levels*					х	Х
Full blood count ¶ (FBC)		Daily while on CYP3A4 inhibitor				
Coagulation, Chemistry, Ferritin, Troponin, Procalcitonin	х	х	x	x	х	х
FiO 2	х	Х	Х	х	х	Х
SpO₂ and/or PaO₂	х	Х	х	х	х	Х
Randomisation		Х				
Weight and Estimated height		Х				
Safety monitoring of liver and renal function	х	Х	Х	Х	х	Х
Length of stay						
Serious Adverse Events	х	Х	Х	х	х	х
Concomitant medications	Х	Х	Х	х	Х	Х
Serum		х		х	Х	х
Plasma		Х		х	Х	Х
RNA in PAXgene tube		Х		Х	Х	Х
PBMC		x		х	х	Х

<sup>+ data that is routinely collected for clinical purposes will be recorded and a visit is not required

<sup># in the event that the patient recovers from COVID19 and is discharged, these visits will not be mandated. Instead a visit should occur on the date of discharge. Where possible, patients will be contacted by telephone at day 7, 14 and 28 and invited to attend for blood tests to monitor resolution of illness.

\*Ruxolitinib dose for these patients will be assessed after 10 dialysis patients complete Day 14 through pharmacokinetics (PK) levels which will be assessed.

<sup>¶For patients randomized to ruxolitinib and prescribed a strong CYP3A4 inhibitor or dual CYP3A4/CYP2C9 inhibitor. Please refer to Section 7.8 for details.

# 9.3 FOLLOW UP SCHEDULE – LONG COVID SUB-STUDY

All participants that agree to take part in the study will either be consented via telephone or in person. The substudy only involves existing participants which have already **consented** to the main study.

Telephone consent process will be an alternative process in case the existing study participants already consented are not able to come back to the clinics anymore.

Participants who take part in the sub-study will be screened for the following:

- Admissions to hospital
- New co-morbidities
- New thrombosis
- Repeat COVID-19 infection
- Number of COVID-19 Vaccinations
- Any ongoing investigations by primary care for long COVID
- Any current chronic infections/acute infections

Patient be asked to complete the following 12 - 24 months after their randomisation to the primary study:

- Fatigue severity scale (FSS)
- MRC Dyspnoea scale
- EQ-5D-5L

	Visit 3
Study Day	Follow up visit 
Consent to sub-study	X*
Medical history including new comorbidities	Х
and current infection	
Concomitant medications	Х
Confirmation of repeated COVID-19	Х
diagnosis, duration and severity	
New thrombosis	Х
Fatigue Severity Scale	Х
MRC Dyspnoea scale	Х
EQ-5D-5L	Х

<sup>1 Last follow up visit may be up to 24 months post randomisation

MATIS version 4.0 dated 2nd November 2022

IRAS: 282552 Page **48** of **57** 

\* Participants will be asked to consent either via telephone call or in person on site by the local PI or the delegated person within the study team, please refer to section 3.4

Imperial College Healthcare

#### 9.4 INCIDENTAL FINDINGS

If there are any incidental findings of any relevance to the participants at any time during their participation in the study, then these will be explained to them. Any incidental findings will be recorded in the clinical notes and will be documented in GP and discharge letters.

# 9.5 LOST TO FOLLOW-UP

The study team will make every reasonable effort to contact participants who have been discharged while on the study to complete the necessary protocol assessments. If any participants are lost to follow-up then the entire data set will be analysed as per the ITT method.

# 9.6 END OF TRIAL

The end of the scheduled treatment phase is defined as the date of the last Follow-up visit of the last participant. The end of the study is the date of the final data extraction from NHS Digital (anticipated to be 10 years after the last patient is enrolled).

#### 10 TRIAL MANAGEMENT

The trial will be coordinated by a Central Coordinating Office within the Department of Haematology staffed by members of the Non-malignant Haematology Clinical Trials Unit.

# 10.1 TRIAL MANAGEMENT GROUP

A Trial Management Group (TMG) will be established, and will include the Chief Investigator [name], the trial statistician and the trial coordinator. Key trial personnel will be invited to join the TMG as appropriate to ensure representation from a range of professional groups. Notwithstanding the legal obligations of the Sponsor and Chief Investigator, the TMG will be responsible for the day-to-day running and management of the trial and will meet by teleconference or in-person as required. Please refer to the TMG Charter for details.

# 10.2 TRIAL STEERING COMMITTEE (TSC)

The Trial Management Group will also serve as the Trial Steering Committee (TSC) and will provide overall trial supervision and provide advice. The ultimate decision for the continuation of the trial lies with the TSC. The TSC will meet at least once a year or more often if required. Please refer to the TSC Charter for details.

#### 10.3 DATA MONITORING COMMITTEE

During the study, interim analyses of all study data will be supplied in strict confidence to the independent DMC, which will comprise an independent statistician. The DMC will request such analyses at a frequency relevant to the emerging data from this and other studies.

The DMC will independently evaluate these analyses and any other information considered relevant. The DMC will determine if, in their view, the randomised comparisons in the study have provided evidence on mortality that is strong enough (with a range of uncertainty around the results that is narrow enough) to affect national and global treatment strategies. In such a circumstance, the DMC will inform the TSC who will make the results available to the public and amend the trial arms accordingly. Unless this happens, the Steering Committee, Chief Investigator, study staff, investigators, study participants, funders and other partners will remain blind to the interim results until 28 days after the last patient has been randomised for a particular intervention arm (at which point analyses may be conducted comparing that arm with the SOC arm).

The Data Monitoring Committee (DMC), will give advice on whether the accumulated data from the trial, together with the results from other relevant research, justifies the continuing recruitment of further patients. Meetings may be called if recruitment is much faster than anticipated and the DMC may, at their discretion, request to meet more frequently or continue to meet following completion of recruitment. An emergency meeting may also be convened if a safety issue is identified. The findings will be conveyed to the MHRA, funders, and/or sponsors as applicable. The DMC may consider recommending the discontinuation of the trial if the recruitment rate or data quality are unacceptable or if any issues are identified which may compromise patient safety.

Please refer to the DMC Charter for details.

# 11 MONITORING

# 11.1 RISKS AND BENEFITS

There is evidence that blockade/inhibition of the JAK/STAT pathway could have a beneficial effect on the CRS and the course of severe respiratory disease/ARDS in patients with COVID-19. However, ruxolitinib has not previously been studied in patients with COVID-19 pneumonia. Therefore, it is unknown as to whether there will be a benefit for patients being treated with ruxolitinib in this disease.

Imperial College Healthcare

Important identified and potential risks from ruxolitinib clinical development and post authorization experience to date include: infections, tuberculosis, use in patients with hepatic impairment and with moderate or severe renal failure or end stage renal failure, elevated transaminases, bleeding, progressive multifocal leukoencephalopathy, adverse events after discontinuation of ruxolitinib, non-melanoma skin cancer, hepatitis B reactivation, and developmental toxicity.

Potential risks for research participants

No disadvantages are anticipated for research participants emanating from taking part in the study.

Potential benefits for research participants

There is no direct clinical benefit for research participants, but the information generated by this study may benefit future patients.

11.2 MONITORING AT STUDY COORDINATION CENTRE

Staff at the Non-malignant Haematology Clinical Trials Unit will review Case Report Form (CRF) data for errors and missing key data points. The trial database will also be programmed to generate reports on errors and error rates. Essential trial issues, events and outputs, including defined key data points, will be detailed in the MATIS trial Data Management Plan.

